3. STUDY DESIGN

This study is a double-blind randomized placebo-controlled parallel trial. A summary of the study set-up and workflow is shown in **Figure 3**.

[figure not shown]

Figure 3 PREDUCTOME study: set-up and workflow

The study consists of the screening, intervention, and the follow-up periods.

During the **screening** period, approximately one hundred and seventy-seven UC patients will be recruited. P-SCCAII score data will be collected to select mild UC patients which is defined as 3-5 points on a 19-point scale. A stool sample will also be provided by patients to determine the Bacteroidetes level by quantitative polymerase chain reaction (qPCR) quantification of the number of total bacteria and Bacteroidetes. Based on the baseline microbiota from a subject in a fecal microbiota transplantation trial [20], in which healthy donors, sustained responding UC patients, and non-responding UC patients had an average relative abundance of 8%, 5%, and 19% Bacteroidetes, respectively, predicted responders are defined as UC patients having with a relative abundance of Bacteroidetes <=10% in their feces, while predicted non-responders are defined as UC patients with a relative abundance of Bacteroidetes >=15% in their feces. A total of sixty screened mild UC patients will continue with this study that consists of thirty predicted responders and thirty predicted non-responders.

To assess the habitual dietary intake of the last month, a validated food frequency questionnaire (FFQ, see F1) will be taken at the baseline. The data will also be used for potential correlation analysis with other parameters as diet is considered an important modulator of the intestinal microbiota. For the intervention, at **baseline**, selected participants

need to fill out several questionnaires including P-SCCAI (once), gastrointestinal symptom rating scale (GSRS, once), stool consistency (Bristol stool scale, daily for 7 consecutive days), stool frequency (daily for 7 consecutive days), short inflammatory bowel disease questionnaire (SIBDQ, once). Information of medication use and adverse events will be extracted from patient record and diary. In addition, they have to collect a stool sample for determining calprotectin level, microbiota composition, and SCFAs profile.

Sustained remission in UC patients in the published fecal microbiota transplantation trial was associated to an increased fraction of butyrate producers [20]. Our *in vitro* incubation studies with fecal inocula from UC patients showed that a prebiotic mixture of acacia gum, partially hydrolyzed guar gum, and resistant starch, showed the highest butyrate boosting capacity in subjects with low fecal Bacteroidetes levels. Hence, demonstrating the perfect candidate for our study.

Based on published studies on interventions on inducing clinical remission, an 8-week intervention should be sufficient for the prebiotics interventions to result in significant effects [4, 16, 27, 28]. An 8-week **intervention** period with four parallel arms:

- 1) predicted responders with prebiotics treatment (acacia gum, partially hydrolyzed guar gum, and resistant starch)
- 2) predicted responders with placebo (maltodextrin and corn starch)
- 3) predicted non-responders with prebiotics treatment (acacia gum, partially hydrolyzed guar gum, and resistant starch)
- 4) predicted non-responders with placebo (maltodextrin and corn starch)

During the intervention period, the subjects will consume the respective supplement (3 grams/sachet, 2 sachets per day, one in the morning and one in the evening). To avoid GI complaints due to a sudden intake of the prebiotics/placebo supplement, there will be a gradual increase in dosage: only 1 sachet will be consumed per day in the first week of the intervention period, followed by 2 sachets per day for the remainder of the intervention. At week 4 and week 8, they will also complete short questionnaires including P-SCCAI (once a week), GSRS (once a week), stool consistency (a 7-day record at each week), stool frequency (a 7-day record at each week), SIBDQ (once a week). Information of medication use and adverse events will be extracted from patient record and diary (once a week). At the end of the intervention period (T= 8 weeks), the participants will provide a second stool sample for fecal calprotectin measurements, microbiota composition, and SCFAs profile analysis. We will determine response with the P-SCCAI score at T= 8 weeks.

The intervention will be followed by a 4-week and 1-year **follow-up** period. At the end of each follow-up (T= 12, and 60 weeks), the participants will collect a stool sample for the same measurements as those at the end of the intervention period (fecal calprotectin level, microbiota composition, and SCFAs profile), and complete the questionnaires including P-SCCAI (once a week). Information of medication use will be extracted from patient record and diary (once a week).

As the intervention will take place at home, the study can be conducted in a merely coronavirus (COVID-19)-proof setting.

4. STUDY POPULATION

4.1 Population (base)

This study will be performed in adult UC patients with mild severity of the disease. UC severity will be determined by P-SCCAI score (see F1) [29], with a 3-5 score on a 19-point scale selected as mild UC inflammatory activity [30, 31]. Call for the participation of this study will be first spread among patients base (more than 1200 IBD patients) of Ziekenhuis Gelderse Vallei in Ede. In case of under-recruitment, UC patients of Rijnstate in Arnhem will be included as well.

In order to be eligible to participate in this study, a subject must meet all of the following inclusion criteria and none of the exclusion criteria.

4.2 Inclusion criteria

1. Male and female subjects aged 18 to 65 years*
2. Body Mass Index (BMI) between 18 and 30 kg/m² (self-reported)
3. Ulcerative Colitis confirmed via previous endoscopy and histology
4. Mild active UC as defined by P-SCCAI score of 3 to 5 (range 0 to 19)
5. Frequent relapse (at least one exacerbation in the last two years)
6. No known allergy to any components of the study product (self-reported)
7. Signed informed consent
8. Stable UC medication defined as no switch to other medication or no dose change
9. Mobile phone on which apps (used for questionnaires) can be downloaded (iOS version 9 and newer, Android version 4.4 and newer. Phones manufactured after 2013 are usually suitable)
10. Stable dietary pattern during the study

* We only include adults (age 18-65) as previous studies have shown that adolescent and elderly microbiota as well as UC presentation in adolescents can be different from adults[32, 33].

4.3 Exclusion criteria

1. Any other underlying disease of the GI-tract or previous bowel surgery, except cholecystectomy and appendectomy
2. Pregnancy or intending to become pregnant during the study
3. Use of medication that can interfere with the study outcomes, as judged by the medical supervisor
4. The need for antibiotic use during the intervention period
5. Systemic antibiotics and proton pump inhibitors (except for omeprazole and pantoprazole with dosage <20 mg), prebiotic supplements, probiotic supplements four weeks prior to study start
6. Currently participating in another intervention study
7. Acquaintances of anyone in the research team

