5. TREATMENT OF SUBJECTS

5.1 Investigational product/treatment

In this study, all 60 participants will undertake an 8-week intervention with either a prebiotics supplement (arm 1 and 3) or a placebo supplement (arm 2 and 4), which will be consumed once per day (1 sachet in the morning) during the first week, and twice per day (1 sachet in the morning and 1 sachet in the evening) for the remainder of the intervention. During the entire trial, research subjects will maintain their normal routines concerning their diet, medication use, and exercise pattern.

Prebiotics supplement: Prebiotics preparation is composed of three individual fibers (40% acacia gum, 20% partially hydrolyzed guar gum, and 40% resistant starch) from Winclove Probiotics B.V. (Amsterdam, the Netherlands).

Placebo (control): Placebo preparation is composed of food-grade corn starch and maltodextrin from Winclove Probiotics B.V. (Amsterdam, the Netherlands).

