At T = 0, 4, and 8 weeks, health-related quality of life will be assessed by the SIBDQ questionnaire (see F1). SIBDQ is a 10 item shortened version of the original IBDQ which was 32 items. It has a seven-point graded scale where 1 represents very troublesome symptoms and 7 represents the absence of troublesome symptoms. Measures quality of life as measured in four domains (bowel symptoms, emotional health, systemic systems and social function) [58]. Its reliability and responsiveness to change has been validated in UC [59].

Medication use

At T= 0, 4, 8, 12 and 60 weeks, information of medication use will be extracted from patient record and diary. It consists of the current medication use (e.g., aminosalicylates, corticosteroids, immunosuppressive agents, antimicrobial agents, and inhibitors of tumour necrosis factor-alpha (TNF- α)). Medication changes at week 4, 8, 12, and 60 provide information on disease development, with a downgrade means improvement and an upgrade means worsening of UC.

Safety parameters

At T= 0, 4, and 8 weeks, safety parameters (i.e., incidence of adverse events) will be monitored by patient record and diary. In this diary, all relapse-relevant information, including the need for systemic steroids, hospitalization, and surgery will be collected.

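### Two eligibility criteria turn on events after randomisation and a third has no time window; with the withdrawal rules, week-8 scores can be lost for outcome-related reasons

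*Protocol*

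**What the plan says.** Protocol section 4.1 makes eligibility all-or-nothing: "a subject must meet all of the following inclusion criteria and none of the exclusion criteria". Section 8.3, under Screening, adds the timing: only people who satisfy the full list are invited to be screened, so the check comes before randomisation.

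Three items on the list matter here.

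- Exclusion 4 (section 4.3): "The need for antibiotic use during the intervention period".
- Inclusion 10 (section 4.2): "Stable dietary pattern during the study".
- Inclusion 8 (section 4.2): "Stable UC medication defined as no switch to other medication or no dose change", with no period given.

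Section 5.1 sets the expected conduct once in the trial: "During the entire trial, research subjects will maintain their normal routines concerning their diet, medication use, and exercise pattern".

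Section 8.1.2 makes medication use a secondary endpoint. The tracked drugs include "aminosalicylates, corticosteroids, immunosuppressive agents, antimicrobial agents", and changes at weeks 4, 8, 12 and 60 are interpreted "with a downgrade means improvement and an upgrade means worsening of UC".

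Section 8.4 lets the investigator withdraw a subject who has to start medication that interferes with outcomes. Section 8.4.1 requires withdrawal for serious gastro-intestinal complaints or an exacerbation. Section 8.6 provides no follow-up after withdrawal, apart from an exception for other medical reasons. Section 8.5 provides no replacement.

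**The concern.** An eligibility criterion should be decidable from what is known when it is applied. Exclusion 4 and inclusion 10 refer to the weeks after the supplement starts, so at entry they can only be guessed. If anyone returns to them later, a randomised patient can be declared ineligible because of something that happened on treatment.

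Such events are not neutral. The protocol itself reads an upgrade in medication as worsening disease and counts antimicrobials among the drugs tracked. A link between antibiotic courses and disease course is plausible; for diet changes it is indirect. If patients with these events lose their week-8 score, and the events are not equally frequent or equally selective in the two arms, the comparison of prebiotics with placebo loses the protection of randomisation. With 15 patients planned per arm, a few lost scores are enough to matter.

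**Working it through.** **1. Can the criteria be judged when they are applied?**

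- Exclusion 4: not as written. Prior antibiotics have their own criterion with a look-back (exclusion 5, ending "probiotic supplements four weeks prior to study start"), so exclusion 4 must concern something else. Exclusion 2 speaks of intending to become pregnant, so the protocol words an intention when it means one; exclusion 4 does not.
- Inclusion 10: not as written. The only diet assessment described is one food frequency questionnaire at T=0 (Summary; section 8.1.3). Stability over the study is never measured, so a later judgement on it would be ad hoc.
- Inclusion 8: cannot be applied consistently, because the period over which there must be no switch or dose change is not given. It reaches past randomisation only if section 5.1 is read into it.

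**2. Is there a route from such an event to a missing week-8 score?**

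Yes, through sections 8.4 and 8.6: interfering medication is started, the investigator may withdraw the patient, and follow-up generally ends. A statistical analysis plan can define analysis sets but cannot recover scores that were not collected.

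**3. Which comparisons are exposed?**

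Section 10.1 lists two sets. The first compares predicted responders with predicted non-responders, both on prebiotics; these groups are defined by Bacteroidetes level and are not randomised against each other. The second compares prebiotics with placebo within each stratum. The loss of randomised protection concerns the second set.

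**4. The planned sample size, which is not disputed**

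Inputs from section 4.4: means 3.5 and 2.8 (difference 0.7), SD 0.5, two-sided alpha 0.05, power 90%, 30% drop-out.

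- n per group = 2 × (1.960 + 1.282)² × (0.5/0.7)² = 10.7, rounded up to 11, as stated.
- 11 × 1.3 = 14.3 gives the stated 15; 11/0.7 = 15.7 would give 16. The difference does not bear on this point.

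**5. Illustration of size**

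Assumptions, none of them in the protocol: normal week-8 scores, and the lost patients are exactly the worst scorers. Removing the top fraction p of a normal distribution lowers its mean by SD × φ(z)/(1−p), where z is the (1−p) quantile.

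- p = 0.20: z = 0.842, φ(z) = 0.280, shift = 0.280/0.80 = 0.350 SD.
- p = 0.10: z = 1.282, φ(z) = 0.1755, shift = 0.1755/0.90 = 0.195 SD.
- Difference: 0.350 − 0.195 = 0.155 SD. At SD 0.5 this is 0.08 points.

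Simulation with 15 per arm, both arms normal with mean 3.5 and SD 0.5, no true effect, two-sided t-test at 5% (20,000 repetitions):

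| Worst scorers lost (one arm, other arm) | Absolute shift in mean difference | Type I error |
|---|---|---|
| 0, 0 | 0.00 | 5% |
| 1, 0 | 0.06 | 7% |
| 2, 0 | 0.12 | 11% |
| 3, 0 | 0.16 | 16% |
| 3, 1 | 0.10 | 12% |
| 4, 4 | 0.00 | 10% |

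The last row shows that equal loss leaves the mean difference unshifted. The test level still rises under this extreme selection, because trimming the worst scores understates the spread.

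**The case against.** The strongest reply is that section 8.3 makes eligibility a gate before screening. No section re-tests it later, and none drops a randomised patient from the analysis for failing it. On that reading exclusion 4 means a need foreseen at entry, inclusion 10 means a willingness to keep to one's usual diet (in line with section 5.1), and inclusion 8 means stable medication on entry. This stands to the extent that a reader might infer from the wording that such patients are removed after randomisation, and the protocol does not say so. Analysis populations may also be defined in a plan not shown, so their absence here is not the point. What remains is that the text does not state the entry-only reading, and a route to lost scores exists in 8.4 and 8.6 however the criteria are read.

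A reader might also see a contradiction between inclusion 8 and the medication endpoint in 8.1.2, with one event serving as both breach and outcome. The documents do not support that. Inclusion 8 gives no period, and as an entry condition it is compatible with recording later changes. Indeed, 8.1.2 presupposes that patients whose medication changes are still observed. The defect is the missing window.

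Finally, one could express the shift as a share of the planned 0.7. That figure is set in section 4.4 for responders versus non-responders on prebiotics, not for prebiotics versus placebo, so the ratio would mix two contrasts.

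It is also fair to say that rewording the criteria alone would leave the withdrawal route intact. The fix therefore has to cover both.

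**Conclusion.** The point holds as a defect of wording combined with a stated route to outcome-related loss. Exclusion 4 and inclusion 10 cannot be known when they are applied, and inclusion 8 lacks a window. Sections 8.4 and 8.6 allow a week-8 score to be lost when interfering medication is started. This can bias the within-stratum comparisons of prebiotics with placebo. It is not shown that exclusion from the analysis is planned.

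The size is unknown. The 0.155 SD (0.08 points at SD 0.5) rests on an assumed 20%/10% split and on losing only the worst scorers. The simulated type I errors of 7% to 16% for one-sided or unequal loss use the same extreme selection and are an upper range for the losses shown. The direction is also open: more loss of bad scores on placebo would understate a benefit, more on prebiotics would overstate it, and equal loss with no treatment effect would not shift the difference. The sample size is unaffected.

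**What to change.** 1. Reword exclusion 4 and inclusions 8 and 10 as facts known or planned at or before randomisation: an antibiotic course under way or foreseen, UC medication unchanged over a stated look-back period whose length the investigators choose, and no planned change of diet.
2. State that later antibiotic use, diet change or medication change is recorded as a post-randomisation event, and that these patients go on giving P-SCCAI data, at least at week 8, and are analysed as randomised.
3. Reconcile sections 8.4 (with 8.4.1) and 8.6 with this, so that leaving treatment does not by itself end outcome collection for patients who still consent. The clinical grounds for stopping the supplement need not change.

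The cost is a short protocol amendment and continued collection of a home-completed questionnaire from a few patients. The small downside is that protocol deviators are included in the analysis, which may dilute a treatment effect somewhat. No change to sample size or treatment is needed.

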4.4 Sample size calculation

The primary objective of the trial is to validate the prediction that a higher response (lower mean P-SCCAI score) is induced at T= 8 weeks by the prebiotics intervention in mild UC patients with low Bacteroidetes levels (predicted responders), but not in those with high Bacteroidetes levels (predicted non-responders) in their gut. Mild UC is defined as a P-SCCAI score of 3 to 5. According to an extensive study regarding UC disease activity conducted in the Netherlands, mild UC patients have a P-SCCAI score of 3.5 ± 0.5 (Mean \pm standard deviation (SD)), and patients in remission score at 1.0 ± 0.33 (Mean \pm SD)[34, 35].

In a series of germinated barley foodstuff (GBF) intervention studies, 10 mild to moderately active UC patients received 30 grams of GBF (equals to 10 grams fiber) daily for 4 weeks [4], and researchers found a significant decrease in clinical activity index scores. In a later study, another group of 11 mildly to moderately active UC patients consuming 20-30 grams of GBF (equals to 6.66-10 g fiber) daily for 4 weeks showed similar results, with decreases in clinical activity index scores [28].

Based on two-sided statistical testing for unpaired continuous data, an $\alpha=0.05$ (chance on type-I error) and $\beta=0.10$ (chance on type-II error), and assuming a 20% difference of mean P-SCCAI score between predicted responders with prebiotics and predicted non-responders with prebiotics, it was calculated that at least 11 subjects per group are needed for the primary outcome P-SCCAI ($\mu_1=3.5$; $SD_1=0.5$; $\mu_2=2.8$). According to previous trials on prebiotics on IBD patients, a 20% of drop-out rate is commonly seen. Given that the intervention duration is 8 weeks long, followed by a 1 year follow-up, higher dropout rate (30%) is expected. To compensate for a 30% drop-out rate, 15 subjects per group are needed.

To reach inclusion of 30 predicted responders and 30 predicted non-responders, we made an estimate how many subjects we need to screen based on the earlier obtained microbial composition of stool samples from UC patients in the Ede area. Around 50% of these subjects were categorized as low Bacteroidetes subjects (predicted responders) and while 17% of them as high Bacteroidetes subjects (predicted non-responders). To include these responders we will need to screen 177 mild UC patients.

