8. METHODS

8.1 Study parameters/endpoints

8.1.1 Main study parameter/endpoint

Response (mean P-SCCAI score) between arms at T = 8 weeks:

At T = 8 weeks (the end of the intervention), the P-SCCAI score will be collected via the P-SCCAI questionnaire. As main endpoint, the mean P-SCCAI score for each arm will be determined and compared to each other to determine the difference in response at T = 8 weeks.

P-SCCAI is derived from the original SCCAI questionnaire by translating into patients' comprehensible language, and has been validated to give substantial agreement with the original SCCAI [54]. P-SCCAI refers to disease symptoms during the previous week. It contains 13 items clustered into six domains: bowel frequency (during the day), bowel frequency (during the night), urgency of defecation, blood in stool, general well-being, and a number of defined extracolonic features of UC (i.e. arthritis, erythema nodosum, pyoderma angrenosum, uveitis).

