8.4 Withdrawal of individual subjects

Subjects can leave the study at any time for any reason if they wish to do so without providing a reason and without any consequences. The investigator can decide (upon consultation with the medical supervisor) to withdraw a subject from the study for urgent medical reasons, such as serious GI complaints, negative reactions upon supplement intake, etc., or when study participants have to start medication that interferes with outcomes during the study period.

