8.4.1 Specific criteria for withdrawal

A subject will be withdrawn from the study in the case of serious gastro-intestinal complaints or an exacerbation of UC reported by the subjects (such as continuous diarrhea or constipation, bloating, abdominal pain).

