10.1 Primary study parameter(s)

Response (mean P-SCCAI score) between arms at T = 8 weeks

To assess the response, data of mean P-SCCAI score within each arm at T = 8 weeks (after the intervention) will be obtained.

Firstly, the mean P-SCCAI score between the predicted responders with prebiotics and predicted non-responders with prebiotics will be compared by using a Student T-test if normally distributed, otherwise a Mann-Whitney U test when skewed.

Secondly, the mean P-SCCAI score between prebiotics and placebo groups within predicted responders or predicted non-responders will be compared by using a Student T-test if normally distributed, otherwise a Mann-Whitney U test when skewed.

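### Section 4.4's 90% power needs 12 completers per arm at SD 0.5, 15 per arm does not offset 30% loss, and the SD comes from a score-defined class, not from week 8

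*Protocol*

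**What the plan says.** Protocol section 4.4 compares predicted responders on prebiotics with predicted non-responders on prebiotics. Its inputs are means of 3.5 and 2.8, SD1 = 0.5, two-sided α = 0.05 and β = 0.10, and it concludes that "it was calculated that at least 11 subjects per group are needed for the primary outcome P-SCCAI". It then expects 30% drop-out, raised from the 20% usual in earlier trials because of the 8-week intervention and the 1-year follow-up, and says that 15 per group compensates for it.

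The SD has one source. Section 4.4 reports that "mild UC patients have a P-SCCAI score of 3.5" with SD 0.5, and states in the same paragraph: "Mild UC is defined as a P-SCCAI score of 3 to 5". The only other SD given is for another class: "patients in remission score at 1.0" with SD 0.33. There is no SD for the second group and none for week 8.

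The endpoint is the score at week 8. Section 8.1.1 says: "As main endpoint, the mean P-SCCAI score for each arm will be determined and compared to each other". In section 10.1 the first primary comparison is that "the mean P-SCCAI score between the predicted responders with prebiotics and predicted non-responders with prebiotics will be compared by using a Student T-test", with a Mann-Whitney test if the data are skewed.

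**The concern.** There are two separate problems.

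First, two figures in section 4.4 do not deliver what the text says of them under its own inputs. Eleven per arm does not reach 90% with the t-test that section 10.1 plans, and 15 per arm does not leave 11 after 30% loss.

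Second, an SD among patients grouped by their score is held down by the grouping itself. The entry band of 3 to 5 limits the score at inclusion. It does not limit the score eight weeks later, and the assumed mean of 2.8 already lies below the band. Using 0.5 in both arms at week 8 is therefore an assumption, and section 4.4 neither labels nor defends it as one.

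What is at stake is how a null result is read. The trial is meant to validate a prediction. If the primary comparison is not significant and the trial is described as having had 90% power, the result looks like evidence against the prediction when power may have been well below that.

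**Working it through.** **Inputs (section 4.4):** difference 3.5 − 2.8 = 0.7; SD 0.5; two-sided α = 0.05; β = 0.10; 15 enrolled per arm; 30% loss, against 20% in earlier trials. Test (section 10.1): Student t-test. SDs above 0.5 are my assumptions.

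**1. Reproducing the 11.** Normal approximation with the same SD in both arms: n = 2 × (1.960 + 1.2816)² × (0.5/0.7)² = 10.72, rounded up to 11. The stated figure reproduces.

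**2. Power of the planned test at SD 0.5.** Noncentral t with 2n − 2 degrees of freedom and noncentrality 0.7/(0.5 × √(2/n)). For n = 11 the noncentrality is 3.28.

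| Completers per arm | Power at SD 0.5 |
|---|---|
| 10 | 84.1% |
| 11 | 87.7% |
| 12 | 90.6% |
| 15 | 95.9% |

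So 12 per arm are needed for 90%.

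**3. Drop-out.**
- 30% loss: 15 × 0.7 = 10.5, so 10 to 11 completers and 84–88% power. Keeping 11 needs 11/0.7 = 15.7, so 16.
- 20% loss: 15 × 0.8 = 12 completers, 91%.
- Averaged over binomial numbers of completers from 15 per arm, power is 84.8% at 30% loss and 89.9% at 20%.

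**4. Sensitivity to the week-8 SD** (difference 0.7, common SD, noncentral t):

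| SD | 11 per arm | 12 per arm | 15 per arm |
|---|---|---|---|
| 0.5 (section 4.4) | 88% | 91% | 96% |
| 0.6 (assumed) | 74% | 78% | 87% |
| 0.8 (assumed) | 50% | 54% | 64% |
| 0.9 (assumed) | 41% | 45% | 54% |
| Largest SD giving 90% | 0.48 | 0.505 | 0.57 |

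**5. Is a wider SD plausible?** If change is unrelated to the starting score, SD 0.5 in the predicted responders on prebiotics means that every such patient falls by the same 0.7 points. Two illustrations keep the mean at 2.8 and leave the other arm at 0.5. Their response shares are assumed.
- (i) 70% improve by 1 point and 30% do not change. Arm variance 0.25 + 0.7 × 0.3 × 1² = 0.46. Pooled SD √((0.46 + 0.25)/2) = 0.60. Power 75% with 11 per arm, 87% with 15.
- (ii) 28% reach the remission class (1.0, SD 0.33) and 72% stay mild (3.5, SD 0.5). Mean 0.28 × 1.0 + 0.72 × 3.5 = 2.8. Arm variance 0.28 × 0.33² + 0.72 × 0.5² + 0.28 × 0.72 × 2.5² = 1.470, SD 1.21. Pooled SD √((1.470 + 0.25)/2) = 0.93. Power 39% with 11 per arm and 51% with 15 by formula; 35% and 49% when the skewed mixture is simulated.

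These illustrations are the reason for ending the assumed range at about 0.9.

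**The case against.** The best defence is that section 4.4 is open about its inputs. The means, the SD and the error rates are printed beside the result, the SD is attributed to mild patients, and the 11 is correct by a common approximation. That stands. A reader might infer that the protocol makes an unconditional claim of 90% power, or that the 11 is a miscalculation; the text supports neither. The gap between 11 and 12 is one subject per arm and about 3 points of power.

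On drop-out, the 30% was set partly for the 1-year follow-up, so loss by week 8 is probably smaller. This also stands, and it is why the powers for 12 and 15 per arm belong beside those for 11.

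On the SD, the documents contain no larger value. If only the predicted responders' arm widens and the other stays at 0.5, a pooled SD of 0.8 needs an SD of √(2 × 0.64 − 0.25) = 1.01 in that arm. A pooled SD of 1.0 needs √(2 × 1.00 − 0.25) = 1.32, which is wider than the extreme illustration (1.21). A reader tempted to carry the range to 1.0, where 11 per arm gives 35%, would go beyond what can be argued from section 4.4.

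Nor does the protocol predict a mixture of response and non-response among the predicted responders. The introduction and objectives place the predicted difference between the low- and high-Bacteroidetes strata, where it is the effect under test. Spread within the arm is plausible, but it is an assumption of this review.

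Withdrawals could also narrow the spread. Section 8.4.1 says: "A subject will be withdrawn from the study in the case of serious gastro-intestinal complaints or an exacerbation of UC reported by the subjects". Section 8.4 allows withdrawal "when study participants have to start medication that interferes with outcomes during the study period", and section 8.6 provides in general for no follow-up afterwards. This may remove some high week-8 scores. It does not limit spread downwards, which is where the predicted effect lies.

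**Conclusion.** The point holds in two parts.

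On section 4.4's own inputs, the planned t-test gives 88% with 11 per arm and needs 12 for 90%. Fifteen per arm does not compensate for 30% loss: it leaves 10 to 11 completers and 84–88% power. At 20% loss it delivers 91%. These are small, certain shortfalls that rest on no outside assumption.

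The larger matter is an unsupported input. SD 0.5 describes patients grouped by a score of 3 to 5 and is applied without comment to unrestricted week-8 scores in both arms. The true week-8 SD is unknown, so the size of the problem is conditional. An SD of 0.6 brings power to 74–87% across 11 to 15 completers, and 0.8 to 50–64%. Even with no loss at all, 90% power holds only up to SD 0.57. Drop-out matters much less than the SD.

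This does not show that the trial is underpowered. It shows that the stated power depends on an SD that the protocol has not justified for its endpoint. Confidence is high for the arithmetic and medium for the direction of the SD.

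**What to change.** Keep 60 subjects and restate section 4.4:

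1. Say that 90% power with the planned t-test requires SD 0.5 and at least 12 completers per arm.
2. Replace the statement that 15 per group compensates for 30% loss with what 15 enrolled per arm delivers at SD 0.5: about 84–88% with 10 to 11 completers (30% loss) and about 91% with 12 (20% loss). Note that the 30% also covers the 1-year follow-up.
3. State that 0.5 is an SD for patients classed as mild, assumed to apply in both arms at week 8, and justify it if data exist.
4. Give power for 11, 12 and 15 per arm over a range of SDs labelled as assumed, for example 0.5 to about 0.9, so that a null result is not read as having had 90% power.

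The cost is wording in one section, with no added patients, visits or data. The downside is that the stated power becomes less favourable, and the risk of low power is disclosed, not removed.
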